After NEN enrolled according to the inclusion criteria for both the control group and experimental group (n= 102), the participants started by signing the informed consent, filled out the demographical data and pre-test as proactive steps before the intervention; many sessions of pre-test data collection and intervention were performed according to the availability of NEN, the arrangement of the hospital's nursing director. The estimated time to fill in the demographical data and pre-test is around 30 minutes. Oermann et al. (2020) addressed that the trainer performs a pre-test assessment to assess the effectiveness of SBLST. The investigators discussed the purpose of the study with the control group and explained to them the procedure to prevent any data contamination and minimize the interpretation of the survey content with the other

Intervention

The control group read the brochure containing a brief guideline about basic life support for 30-60 minutes before taking the post-test. Standard treatment ran from Dec 2022 to Jan 2023. One full day for SBLST intervention, from 5 to 7 hours for SBLST intervention is required based on the recent research and uses AHA-2020 guidelines. The number of participants was ten NEN in each session. The

interventional treatment consists of theoretical and practical parts. The SBLST intervention was conducted in an educational lab according to the hospital's capability; SBLST ran for seven days, from 22 Nov 2022 to 20-Dec, 2022.

Researchers combined two frameworks in the SBLST. Miller's Pyramid and Kolb's Cycle; Miller's Pyramid focuses on teaching theoretical and practical aspects of the task through simulation and allowing trainees to perform the procedure independently with guidance; Kolb's Cycle suggests giving learners a scenario to practice until they eliminate errors before moving to another scenario. The SBLST intervention was reviewed by three experts in BLS and approved by the Jordanian Ministry of Health-Life Support Center. It was found to be compliant, safe and covered all aspects of AHA-2020. English experts provided feedback to improve clarity. A pilot study was conducted on 20 nurses to calculate SBLST time, identify errors, monitor the progress and calculate Cronbach's Alpha.

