Adult half-body manikin and a pediatric full-body manikin are necessary; with lung bag inflation and deflation characteristics, palpable carotid pulse, the chest includes spring inside to facilitate chest recoil, and chest compression board, bag-valve-mask-ventilation, chest compression performed on the Charlie simulator to relieve choking. The principles investigator (PI) had a master's degree in critical care nursing, eighteen years of experience between ICUs, lecturers and clinical instructors, valid BLS and ACLS, training of trainers in nursing education, and randomized control trial training. The facilitator must have CPR certifications in BLS and ACLS, enough expertise in education and training, and good communication skills the investigator had a master degree in critical care. Two research assistants supported the

PI in collecting data; one research assistant for the control group and the other for the interventional group.

Post-test

All participants completed the immediate post-test-1 after the interventions. The post-test-2 was conducted by providing the participants with a Google Form Platform link through their phone and email addresses. The post-test after three months evaluates whether the participants' level stayed at the same level or minimized by comparing the mean value between all post-tests. Forty-eight participants in the experimental group completed post-test-2 with a response rate of 94%, and 45 participants in the control group with a response rate of 88%.

Sample Size Estimation

Sample size calculation is performed by using G*POWER software (version 3.1); sample size calculation is summarized and consists of the following steps (1) Select the test family (F-test family), (2) Select the statistical test (Select ANOVA-repeated test, between factors), the preliminary test analysis the researchers used in this study, the rationale for using the Select ANOVA-repeated test between factors due to measure many dependent variables means at different time points. (3) The parameters selected to calculate sample size include one side tail, alpha (α) and equals (0.05)- type one error, Power (P) and equal (0.8), effect size, the number of groups is two (each group = $n/2$) n = the estimated sample size, number of measurements were four measurements (Pre-test, Post-test immediately, Post-test after two months, and Post-test after three months).

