Effect Size (ES) = 0.26, automatically calculated by G*Power software, depending on the sample size of the previous study, the effect size is calculated, the

Control group's post-test result $M \pm SD$ was equal (25.03 ± 3.04) with a sample size of 28 participants, and the interventional group (26.64 ± 2.64) with sample size 29 participants. The sample size is 72 participants; because the research study continued for three months, we added a 10% drop rate for each month, so the drop rate is 30%. Final sample size estimation including drop rate ($n \setminus (1 - \text{dropout rate}) = 72 / (1 - 0.30) = 102$ participants, the intervention group arm is 51 participants, and The largest sample size was obtained from the interventional group, more than the Control Group and the Control group arm 51 participants.

Simple Random Sampling of the Participants

After obtaining ethical approval and permission to conduct the study from the Ministry of Health in Jordan, approval letter (Education/Info\ 15177) and ethical approval letter (MOH/REC/2022/340), The researchers started the formal face-to-face visits to arrange with the nursing director and a continuous education office in the selected hospitals about the study objective and how the study would proceed; The researchers received the activation letter to initiate the study and prepared the list of the available participants who met the study's eligibility criteria. The number of participants depends on the availability of newly employed nurses in the institution who meet the inclusion criteria. The researchers randomly selected the participants from the participants' list by randomly sampling from newly employed nurses in each hospital for interventional and control groups.

. The response of the control group hospitals was as the following; the nursing director and continuous education in AL-Zarqa Governmental Hospital responded by providing all the information about participants and selecting a time and day to perform the Pre-test, standard treatment and the immediate post-test. Prince Hamzah Hospital and AL-Basheer Hospital gave the researcher the names of departments in the

hospital, including those with NEN, and we visited these departments to select the available NEN randomly and performed Pre-test, standard treatment, and immediate post-test in their departments.

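### Post-test-2 went out as a link while the earlier tests were on site, so within-arm change to post-test-2 in knowledge and practice cannot be read as retention or decay

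*Protocol*

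**What the plan says.** **Post-test-2.** The Post-test section of the protocol says: "The post-test-2 was conducted by providing the participants with a Google Form Platform link through their phone and email addresses". It gives the purpose in the next sentence: "The post-test after three months evaluates whether the participants' level stayed at the same level or minimized by comparing the mean value between all post-tests".

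**Earlier tests, control arm.** The section on simple random sampling places these at the hospital. At two hospitals the team "performed Pre-test, standard treatment, and immediate post-test in their departments". The third hospital cooperated by "selecting a time and day to perform the Pre-test, standard treatment and the immediate post-test".

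**Earlier tests, SBLST arm.** The setting is not stated outright. The Study Process section says "many sessions of pre-test data collection and intervention were performed according to the availability of NEN" and "The SBLST intervention was conducted in an educational lab according to the hospital's capability". The Post-test section adds "All participants completed the immediate post-test-1 after the interventions". A test taken straight after a session in a hospital training lab was very probably taken there.

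**Instruments.** Knowledge is scored from 13 multiple-choice items and practice from 10, with one mark for each correct answer. Confidence is seven self-rated percentages. Google Forms was the data collection platform for the study generally.

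**Analysis.** SAP section C computes Cohen's d from pre-test to post-test-2 in each arm and uses it to decide which method works better. It also provides for comparing the two arms after the intervention. Section B applies repeated-measures ANOVA across all tests. Neither document mentions the change of setting.

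**The concern.** A three-month test measures retention only if it is taken under the same conditions as the test it is compared with. Here the form stays the same, but the place, the timing and the presence of staff do not. A nurse answering a link may look up an answer or ask a colleague, and may also lack help that was available on site. Either can move a multiple-choice score without any change in what the nurse remembers.

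Three planned readings depend on this: the protocol's question whether the level held or fell after post-test-1; the per-arm d from pre-test to post-test-2 in SAP section C; and the part of hypothesis v that sets the pre-test against post-test-2. The time effect in the repeated-measures ANOVA carries the same ambiguity. At stake is a published statement that learning was kept or lost, or that one method is better, which partly reflects how the last test was delivered.

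**Working it through.** **1. The stated figures for the remote test.** The documents give 51 nurses per arm and 48 (SBLST) and 45 (control) completers.

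- SBLST: 48 / 51 = 94.1%, stated as 94%.
- Control: 45 / 51 = 88.2%, stated as 88%.

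Both reproduce. They also show that post-test-2 has already been collected.

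**2. Do time and setting overlap completely?**

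| Test | Timing | Control | SBLST |
|---|---|---|---|
| Pre-test | before treatment | on site (stated) | on site (inferred) |
| Post-test-1 | immediate | on site (stated) | on site (inferred) |
| Post-test-2 | three months | link | link |

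No group of nurses is described as taking a late test on site or an early test by link. The observed within-arm change is

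observed change = true change + b,

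where b is the effect of setting. There is one observed quantity and two unknowns, so the data cannot identify either.

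**3. Illustration for one arm.** All values here are assumed. On the 13-item knowledge score, let the true change from post-test-1 be -2 items.

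| b (items) | Observed change |
|---|---|
| -1 | -2 - 1 = -3 |
| 0 | -2 |
| +0.5 | -1.5 |
| +1 | -1 |
| +2 | 0 |

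**4. The between-arm difference at three months.** Let T_I and T_C be the true means in the SBLST and control arms. A setting effect common to both arms cancels: (T_I + b) - (T_C + b) = T_I - T_C.

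It does not cancel if it acts on wrong answers only. Suppose a share q of wrong answers is corrected by look-up, so that observed = T + q(13 - T). The gap becomes (1 - q)(T_I - T_C). Assume post-test-1 means of 11 and 8 and a true loss of 2 in each arm, so T_I = 9, T_C = 6 and the true gap is 3.0.

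| q | SBLST observed (change from post-test-1) | Control observed (change from post-test-1) | Gap |
|---|---|---|---|
| 0.10 | 9.4 (-1.6) | 6.7 (-1.3) | 2.7 |
| 0.25 | 10.0 (-1.0) | 7.75 (-0.25) | 2.25 |
| 0.50 | 11.0 (0.0) | 9.5 (+1.5) | 1.5 |

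In this model the gap shrinks but keeps its sign. The within-arm changes, all truly -2, are distorted by different amounts in the two arms.

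**5. Ranking the arms by within-arm d.** Write D for an arm's true change from the pre-test and s for its standardiser. With a common b, the two values of d differ by

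(D_I / s_I - D_C / s_C) + b(1 / s_I - 1 / s_C).

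Each d contains b in full, and b drops out of the comparison only if s_I = s_C. A comparison of the arms at one time point has no such term when b is common.

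**The case against.** The best case for the plan has four parts.

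- **No contrast in supervision is stated.** The documents describe no closed-book rule, time limit or proctoring for any test, and the platform is the same throughout. This stands. What the text supports is a move from on site to a link, and even the on-site part is inferred in the SBLST arm. That the remote test was unsupervised is also an inference from its delivery.
- **The direction is open.** A reader might infer that look-up at home hides decay. The documents do not support that. Control nurses read the brochure just before post-test-1, and nothing says it was put away first. The section on the languages of the tools says assistants clarified or translated points, which may have been easier on site. Either could raise post-test-1 and exaggerate decay.
- **Both arms took post-test-2 by the same route.** A reader might infer that the three-month comparison of arms is biased, the more so if control nurses kept the brochure. Setting is not confounded with arm, and retention of the brochure is conjecture from silence. The comparison is affected only if the setting effect differs by arm.
- **The reach is limited.** No hypothesis tests post-test-1 against post-test-2, and self-rated confidence has no answers to look up. Both are true. But the Post-test section states the retention question as the purpose of the three-month test, and hypothesis v and SAP section C both use the change from pre-test to post-test-2.

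None of this separates time from setting within an arm.

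**Conclusion.** The point holds for within-arm change in knowledge and practice from an earlier test to post-test-2. Forgetting or retained learning cannot be told apart from the change of setting, because the two coincide for every nurse. This rests on post-test-1 and the pre-test having been on site, which is stated for control and strongly implied for SBLST.

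Neither the sign nor the size of the effect can be taken from the documents. The item counts above are illustrations on assumed inputs and do not estimate what happened. The between-arm difference at three months remains usable with a caveat: if look-up corrects more wrong answers in the weaker arm, the difference shrinks, in the illustration from 3.0 items to between 2.7 and 1.5. The point does not extend with the same force to confidence.

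**What to change.** - **Protocol, Post-test section.** Describe post-test-2 as a score on a remotely delivered online test. State that the change from post-test-1 in knowledge or practice within an arm is not interpreted as retention or decay.
- **SAP section C.** Do not use the within-arm d from pre-test to post-test-2 to decide which method is more effective. Use the between-arm comparison at each time point, where both arms share the test setting, and report post-test-2 with the caveat that the setting effect may differ by arm. The section already foresees comparing the arms after the intervention, so no new method is needed.
- **SAP section B and hypothesis v.** Attach the same limitation to any time effect or pre-test comparison that involves post-test-2.
- **Any repeat or extension.** Give all tests under the same conditions.

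Return visits for this cohort are no longer an option, since 48 and 45 completed tests are already reported. The changes cost only wording. The downside is a weaker statement about retention.

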DEVELOPMENT, VALIDATION, AND
EVALUATION OF THE EFFECTIVENESS OF
SIMULATION IN BASIC LIFE SUPPORT TRAINING
(SBLST), ON NEWLY EMPLOYED NURSES IN
GOVERNMENTAL JORDANIAN HOSPITALS

Study Protocol

Last update On 20-4-2023

Malaysian Human subjects protection review board date: 20-4-2023

Study title:
DEVELOPMENT, VALIDATION, AND EVALUATION OF THE
EFFECTIVENESS OF SIMULATION IN BASIC LIFE SUPPORT TRAINING
(SBLST) ON NEWLY EMPLOYED NURSES IN GOVERNMENTAL
JORDANIAN HOSPITALS

Objective

The general objective of this study is to develop, validate and evaluate the effectiveness of simulation in basic life support training (SBLST) among newly employed nurses in Jordanian governmental hospitals; the study design is a basic experimental study design, randomized control trial (RCT) design, the dependant variables measure in this study; knowledge, practice and confidence by using a pre-test and two follow up tests, two groups are participating in this study; experimental and control group. The control group treatment is the standard intervention (brochure), and the experimental group intervention is a simulation in basic life support training (SBLST); researchers' hypothesized that there are no significant differences between the control and experimental group in the inclusion criteria and pre-test score; furthermore, the simulation in basic life support training intervention significantly improves knowledge, practice and confidence level among newly employed nurses (NEN) in Jordanian governmental hospitals; moreover, there is a significant difference between control and experimental group in the post-test scores in all dependant variables. The study process includes four steps

- Perform the pre-test (assess knowledge, practice confidence surveys)
- Education intervention knowledge and practice
- Perform the post-test 1 (assess knowledge, practice confidence surveys)
- Perform post-test 2 (assess knowledge, practice confidence surveys)

Research Hypotheses

- i. The simulation in basic life support training intervention effectively improves knowledge among newly employed nurses (NEN) in Jordanian governmental hospitals.
- ii. The simulation in basic life support training intervention effectively improves practice among newly employed nurses (NEN) in Jordanian governmental hospitals.
- iii. The simulation in basic life support training intervention effectively improves the confidence level among newly employed nurses (NEN) in Jordanian governmental hospitals.

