- iv. There is no significant difference in means between the pre-test among the newly employed nurses (NEN) among interventional and the control groups in all dependent variables.
- v. There is a significant mean difference between PRE-SBLST and all POST-SBLST results among NEN in all dependent variables.

Study Design

The study design was a prospective, longitudinal, single-blind basic experimental design, randomized control trial (RCT) design.

Study Location

The study was carried out in Jordan; Amman and Al-Zarqa City. The accessible population was NEN in five hospitals. The researchers selected three Jordanian hospitals. The selection was according to the capacity, capability of the institution and eligibility criteria. Computer-generated randomization (Random Allocation Software, version 1.0) was applied in blocks to allocate the hospitals by distributing them into two arms. The first arm was the control group; selected from three hospitals; Prince Hamza Hospital, AL-Basheer Hospital, and AL-Zarqa Governmental Hospital (n=51); the second arm was the interventional group from two hospitals; Prince Faisal Governmental Hospital and Dr.Jameel AL-Totanji Hospital.

Randomization of the Hospitals

To prevent data contamination between the control and interventional groups, computer-generated randomization (Random Allocation Software, version 1.0) was applied in blocks to allocate the hospitals by distributing them into two arms. The first arm was the control group; selected from three hospitals; Prince Hamza Hospital, AL-Basheer Hospital, and AL-Zarqa Governmental Hospital (n=51); the second arm was the interventional group from two hospitals; Prince Faisal governmental hospital and Dr.Jameel AL-Totajji hospital. The control and interventional groups were selected from different hospitals because the researchers are always worried about data contamination and try to minimize it between the control and intervention groups; if the sample was selected from the same area and both groups worked closely together, the data would be contaminated.

Inclusion Criteria

The researchers tried to maintain homogeneity and minimize any variations among the participants by

1. selecting both interventional and control groups from newly employed nurses
2. Male and female participants
3. Participants only who understand the questionnaires and interventions in English

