4. Participants who were previously on-seat undergraduate nursing students last two years, 2020 (4th year nursing bachelor level) and 2021 (3rd year nursing bachelor level) in the period of COVID-19 pandemic and receive basic and clinical learning by online method, and now became a newly employed nurse (NEN) in hospitals and delivered care to the patient.
5. Participants can attend five to seven hours of SBLST session.
6. For more control, we selected nurses who rarely face CPR and do not attend BLS raining the last two years.

Exclusion Criteria

1. The researchers excluded the NEN participants working in intensive care units because ICU nurses face CPR and perform BLS daily.
2. Excluded participants with medical or physical health problems (e.g., pregnant women and participants complaining of lower back pain).
3. Participants who attended CPR training less than two years previously were also excluded. Finally,
4. NEN who upgraded their educational degree from a diploma to a bachelor's degree were excluded.

Research Instruments

The study consists of a pre-test, intervention, immediate post-test-1 after the intervention, and finally, the post-test-2 three months after the intervention. This study measured knowledge, practice, and confidence through pre- and post-tests in control and experimental groups. This study used two interventions: SBLST for the interventional group and AHA-BLS 2020 brochure as a standard treatment for the control group. Data collection proceeded using the Google Form Platform (A web-based instrument Copyrighted by Google application).

The evaluation process includes a pre-test and two follow-up assessments to measure knowledge, practice and confidence. The researcher will analyse the means of each test; the total dependent variables were 30 questions listed in.

Languages of the Tools

According to the HCP educational level, all four sections of the tools assessment are written in English; furthermore, the researchers' assistance clarified any misunderstanding points or need for translation to the participants.

Tools Sections

The tools consist of five sections; research information sheet and consent forms, demographical data, knowledge assessment tools, skills assessment tools, and confidence level assessment tools.

Research information sheet and Consent Forms

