DEVELOPMENT, VALIDATION, AND
EVALUATION OF THE EFFECTIVENESS OF
SIMULATION IN BASIC LIFE SUPPORT TRAINING
(SBLST) ON NEWLY EMPLOYED NURSES IN
GOVERNMENTAL JORDANIAN HOSPITALS

Statistical Analysis Plan

Last update On 20-4-2023

Malaysian Human subjects protection review board date: 20-4-2023

Statistical Analysis Plan

Introduction

The data will be collected through the Google Forms platform, and the researchers will extract the data responses from Google Forms as an Excel sheet (Microsoft Office 2016); all the quantitative data will be coded and transferred to IBM SPSS version 27; the data will be analyzed by using (1) descriptive and (2) inferential statistic.

1. Descriptive Statistics

The descriptive statistic will illustrate the homogeneity and characteristics of NEN in the control and experimental group, including the number and percentage of participants for each group. Also, it will be used to describe statistics for participants' knowledge, practice and confidence level mean percentage in the pre-test and post-test scores.

2. Inferential Statistics

A. Independent T-test

Independent T-test will be used to identify the homogeneity or heterogeneity between pre-tests and post-tests in the control and experimental groups in all dependent variables by interpreting the *P*-value and comparing means (SD). The researchers plan to use independent T-tests despite the normality assumption not being fulfilled depending on the central limit theorem, which states that if samples are more than 30 participants in each group, the researcher can use mean and SD.

B. Repeated Measures-ANOVA

The researchers will use "Repeated Measurement ANOVA" for inferential statistics of the mean of the dependent variables between the interventional and comparator groups in all pre-test and post-tests. Finally, the researchers compared the

*

“Mean,” “Standard Deviation,” and significant level (*P*-value) between tests to explore the effectiveness of the intervention SBLST.

In this step of the analysis, the researchers want to estimate a good idea about the outcomes and how SBLST is considered a good intervention or not after comparing the knowledge score, practice score, and confidence level in both interventional and control groups. The researchers selected a *P*-value < 0.05 for statistical analysis significant to accept the alternative hypothesis or reject the null hypothesis.

C. Effect Size (Cohen’s Score)

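### The sample size is calculated for four measurements, but the described design has three, and the correlation and SD behind the calculation are not stated

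*Protocol*

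**What the plan says.** The Protocol, Sample Size Estimation, uses G*Power's repeated-measures ANOVA, between factors, with two groups, alpha 0.05 and power 0.8. It enters four occasions: "number of measurements were four measurements (Pre-test, Post-test immediately, Post-test after two months, and Post-test after three months". It then gives "Effect Size (ES) = 0.26, automatically calculated by G*Power software", based on a previous study's post-test scores (control 25.03 ± 3.04, n = 28; intervention 26.64 ± 2.64, n = 29), and concludes "The sample size is 72 participants". A 30% dropout allowance brings this to 102, or 51 per arm.

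Elsewhere the design has three occasions:

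- Objective: "knowledge, practice and confidence by using a pre-test and two follow up tests".
- Research Instruments: "The study consists of a pre-test, intervention, immediate post-test-1 after the intervention, and finally, the post-test-2 three months after the intervention".
- Post-test: only post-test-1 and post-test-2 appear, with the result "Forty-eight participants in the experimental group completed post-test-2 with a response rate of 94%, and 45 participants in the control group".

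The SAP, under Effect Size, goes no further than post-test-2. No section describes, cancels or explains a two-month test.

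**The concern.** The number of measurements is a direct input to the between-factors calculation. For a given effect size and correlation, more occasions mean a more precise participant average and a smaller required sample. If the trial takes three measurements, 80% power at 72 describes a schedule with one more assessment than the trial has.

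The correlation between measurements is also an input, and it is not reported. Nor is the SD used to turn the previous study's means into f. Without these, a reader cannot work out what power 72 has with three measurements. What is at stake is the power that the trial reports, since enrolment is complete.

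**Working it through.** **Inputs from the documents:** alpha 0.05, power 0.80, two equal groups, f = 0.26, N = 72, enrolled 102 (51 + 51), post-test-2 completers 48 + 45 = 93. The text calls the test one-sided, but an F test has no one-sided form. Alpha 0.05 on the F test is what reproduces 72; at alpha 0.10, with the other inputs of step 2, N would be 58.

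**Assumption:** the correlation ρ is not given. I take 0.5 and show 0.3 to 0.7, with equal correlation between all occasions.

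**Formula:** noncentral F with 1 and N − 2 degrees of freedom and λ = (2f)² × (n₁n₂/N) × m / (1 + (m − 1)ρ), where m is the number of measurements. With equal arms this is f² × N × m / (1 + (m − 1)ρ). The required N is the smallest even N with power of at least 0.80.

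**Step 1, effect size.** (26.64 − 25.03)/3.04/2 = 1.61/6.08 = 0.2648, which rounds to the printed 0.26. The pooled SD of 2.843 gives 1.61/2.843/2 = 0.283, which rounds to 0.28, so I do not use it.

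**Step 2, reproduce 72.** With m = 4, ρ = 0.5 and f = 0.2648, λ = 0.2648² × 72 × 4 / 2.5 = 8.08 and power is 80.0%. The required N is 72, an exact match. With f = 0.26 as printed, the required N is 76, and 72 gives 78.6%.

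**Step 3, change only m to 3.** With f = 0.2648, λ = 0.2648² × 72 × 3 / 2 = 7.57. The required N is 78, and 72 gives 77.5%. With f = 0.26, the required N is 80, and 72 gives 76.0%.

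**Step 4, is 72 evidence of four measurements?** Not by itself. Three measurements with f = 0.26 and ρ = 0.4 also return 72 (power 80.2%). Only the sentence in the Protocol shows that four was entered.

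**Step 5, numbers actually obtained, three measurements, the plan's own model:**

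| N | ρ = 0.5, f = 0.26 | ρ = 0.5, f = 0.2648 | Range, ρ 0.3 to 0.7, both f |
|---|---|---|---|
| 72 | 76.0% | 77.5% | 68–86% |
| 93 (48 + 45) | 85.9% | 87.1% | 79–93% |
| 102 (51 + 51) | 89.0% | 90.0% | 83–95% |

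With four measurements, 93 would give 89.1% (f = 0.2648, ρ = 0.5). The discrepancy therefore costs 89.1 − 87.1 = 2.0 points at the number of completers.

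**Step 6, a caveat on the model.** The sized test averages the group difference over all occasions, so it assumes the full difference at the pre-test too. Its f comes from a post-test difference, while hypothesis iv expects "There is no significant difference in means between the pre-test among the newly employed nurses (NEN) among interventional and the control groups". If the pre-test difference is zero, the averaged difference is 2/3 of the full one with three occasions and 3/4 with four, and λ is multiplied by the square of that fraction. At ρ = 0.5 with three measurements, power is 53–54% at 93 and 56–58% at 102. With f = 0.2648 at N = 72, averaging over the pre-test takes power from 80.0% to 55.7% with four measurements still in place; going to three then takes it to 44.0%. None of these figures includes clustering by hospital.

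**The case against.** The strongest reply is that the discrepancy changes nothing in practice. The trial allowed for 30% dropout and lost 9 of 102, about 9%. On the plan's own model and ρ = 0.5, the 93 completers exceed the 78 to 80 that three measurements need, and their power is above 80%. Post-test-2 response is already reported, and no decision on enrolment remains. This stands, and it limits the point to one of reporting. It does not remove the contradiction: a stated input disagrees with the design, and over ρ from 0.3 to 0.7 the power at 93 dips to 79%, so the unstated correlation does matter.

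A second reply is that the lower figures in Step 6 belong to a different question. That is largely right. The SAP's repeated-measures ANOVA is for "inferential statistics of the mean of the dependent variables between the interventional and comparator groups in all pre-test and post-tests", but it does not say whether the group effect or the group-by-time interaction decides. It also plans independent t-tests on the post-test scores, whose power does not depend on the number of measurements. The low powers apply only to the between-factors main effect with no pre-test difference, and most of the fall comes from the choice of test.

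A reader might go further and infer that a planned two-month assessment was dropped. The documents do not say so; the four-measurement sentence may simply be an error. A reader might also infer from the exact match in Step 2 that 72 can only be a four-measurement figure. Step 4 shows that it cannot be identified this way.

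**Conclusion.** The contradiction is real: the sample-size paragraph uses four measurements and the described design has three. The stated 72 at 80% power rests on an input that the design does not have, and it cannot be checked without the correlation and the SD behind f. At an assumed ρ of 0.5, moving to three measurements raises the required N from 72 to 78 (f = 0.2648) or from 76 to 80 (f = 0.26). In each case that is a loss of about 2.5 points of power at 72.

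The documents do not support the stronger conclusion that this discrepancy leaves the trial underpowered. On the plan's own model it costs about 2 points at the number of completers. That model ignores clustering and assumes a full pre-test difference, so its 86–90% at 93 and 102 should not be read as assurance of adequate power either. The severity is minor.

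**What to change.** - Reconcile the number of measurements in Sample Size Estimation with the three-assessment design. The authors should confirm whether a two-month post-test was ever planned or done. An explanatory note is enough and keeps the record of the calculation.
- State the correlation that was entered, and the SD and unrounded value behind f = 0.26.
- Restate power for three measurements at the fixed 102 enrolled and 93 completers over a range of correlations, for example 0.3 to 0.7.
- Add a caveat that these figures ignore clustering by hospital and assume the full post-test difference at every occasion. Note that the power of the between-factors main effect is lower if there is no pre-test difference, and that this comes mainly from the choice of test.

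No further enrolment or data collection is needed. The cost is one note and one recalculation, and a stated power that visibly depends on its assumptions.
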